16.3.1 Physician Recommended Monitoring Interval Data

Listing 13: 16.3.1 Primary Physician Recommended CMV Monitoring Intervals

[Implementation Note: In the CSR, Participant ID should be USUBJID (not PATID) for purposes of de-identification. Listing should be sorted by Intervention Group, Participant ID, Visit and Date CMV Monitoring Interval Defined. If "Other" is specified for the recommended monitoring interval, then display "Other: [SPECIFY]" where [SPECIFY] is the text entered in the "If Other, specify:" field.]

Intervention Group	Participant ID	Transplant (Study Day)	Enrollment (Study Day)	Visit (Study Day)	CMV Monitoring Interval Defined (Study Day)	Recommended Monitoring Interval
[e.g. DBS, SOC]		XXX	XXX	XXX	XXX	[e.g. Weekly, Biweekly, Monthly, Quarterly, Other:[SPECIFY]]

16.4.1 Concomitant Medications

Listing 14: 16.2.9 Concomitant Medications

[Implementation Note: "Medication Start Day" and "Medication End Day" are relative to enrollment (which is Day 1, day before enrollment is Day -1).

If ongoing, display "Ongoing" in the "Medication End Day" column. In the CSR, Participant ID should be USUBJID (not PATID) for purposes of deidentification. Sort order: Intervention group, Participant ID, and CM Number.]

Intervention group	Participant ID	CM Number	Medication	Medication Start Day	Medication End Day	Indication	ATC Level 1 (ATC Level 2)
[e.g. DBS, SOC, Observational]		XXX		XXX	XXX		

16.5.1 Questionnaire Data

Listing 15: 16.5.1 Participant Questionnaire After Training

[Implementation Note: In the CSR, Participant ID should be USUBJID (not PATID) for purposes of de-identification. Sort order: Question (in the order of the questionnaire), Participant ID.

Response will be formatted value of the questionnaire question. For questions where participants are asked to describe their result, format as "Yes: [REASON]".]

Question	Participant ID	Study Day	Response
			[e.g. Strongly Disagree, Disagree, etc.]

Listing 16: 16.5.2 Participant Questionnaire 1-Month Post Discharge

[Implementation Note: In the CSR, Participant ID should be USUBJID (not PATID) for purposes of de-identification. Sort order: Question (in the order of the questionnaire), Participant ID.

Response will be formatted value of the questionnaire question. For questions where participants are asked to describe their result, format as "Yes: [REASON]".]

Question	Participant ID	Study Day	Response
			[e.g. Strongly Disagree, Disagree, etc.]

Listing 17: 16.5.3 Participant Questionnaire After Study Completion

[Implementation Note: In the CSR, Participant ID should be USUBJID (not PATID) for purposes of de-identification. Sort order: Question (in the order of the questionnaire), Participant ID.

Question	Participant ID	Study Day	Response
			[e.g. Strongly Disagree, Disagree, etc.]

Listing 18: 16.5.4 Provider End-of-Study Questionnaire

[Implementation Note: In the CSR, Participant ID should be USUBJID (not PATID) for purposes of de-identification. Sort order: Question (in the order of the questionnaire), Participant ID.

Question	Participant ID	Study Day	Response
			[e.g. Strongly Disagree, Disagree, etc.]

APPENDIX 4. WORKED EXAMPLES OF NUMBER OF EXPECTED TESTS

For a given participant, the number of expected tests is derived based on the start dates of the intervals as follows:

Notation:

- 1. Let $t_{i,0}$ denote the date of discharge for participant *i*
- 2. Let $c_i \in \{0, 1, ...\}$ denote the number of times participant *i*'s recommended monitoring interval was changed by their primary care physician during the study period, defined for each participant as the time from enrollment to the earlier of Protocol Completion and Early Termination.
- 3. Let $t_{i,1}, ..., t_{i,c_i}$ denote the times at which the recommended monitoring interval was changed for participant *i*. $t_{i,1}$ is the end date of the initial interval for participant *i*.
- 4. Let t_{i,c_i+1} denote the end of the monitoring period for participant *i*. This is the earlier of the end of the study period or the date after which recommended monitoring is no longer required.
- 5. Let $d_{i,1}, ..., d_{i,c_i}$ denote the corresponding number of days between recommended monitoring tests when the recommended frequency is changed at times $t_{i,1}, ..., t_{i,c_i}$. The days $d_{i,j}$ take the value 7 if recommended frequency is weekly, 14 if the frequency is bi-weekly, 30 if the frequency is monthly and 90 if the frequency is quarterly, 3.5 if the frequency is twice a week, and 17.5 if the frequency is every 2-3 weeks. The initial recommended monitoring frequency should be weekly so the number of days between tests, $d_{i,o}$, should be 7.
- 6. Let $I_{i,j}$ denote the recommended monitoring interval for the j^{th} change to the recommended frequency for participant *i*. The recommended monitoring interval(s) for participant *i* are therefore

$$I_{i,0} = [t_{i,0}, t_{i,1}], I_{i,1} = (t_{i,1}, t_{i,2}], \dots, I_{i,c_i} = (t_{i,c_i}, t_{i,c_i+1}]$$

The number of expected tests in the first interval is calculated as follows. It is assumed that the first expected test is $d_{i,0}$ days after $t_{i,0}$. Let $n_{i,0}$ denote the number of expected tests during $I_{i,0}$. Then,

$$n_{i,0} = floor\left(\frac{t_{i,1}-t_{i,0}+1}{d_{i,0}}\right).$$

Let $m_{i,0}$ denote the date of the last expected recommended monitoring test for participant *i* during interval I_{i0} . Then,

 $m_{i,0} = t_{i,0} + d_{i,0} n_{i,0}.$

There are two possibilities for changes in the monitoring frequency:

1. Frequency in interval $I_{i,j}$ is less frequent than in $I_{i,j-1}$, i.e. $d_{i,j} > d_{i,j-1}$

If the frequency in interval $I_{i,j}$ is less frequent than in $I_{i,j-1}$, i.e. $d_{i,j} > d_{i,j-1}$, then the first test in interval $I_{i,j}$ should occur $d_{i,j}$ days after the last expected test in interval $I_{i,j-1}$. The number of expected tests in interval $I_{i,j-1}$ is calculated from the last expected test in interval $I_{i,j-1}$:

$$n_{i,j} = floor\left(\frac{t_{i,j+1} - m_{i,j-1}}{d_{i,j}}\right), \text{ and}$$
$$m_{i,j} = m_{i,j-1} + d_{i,j}n_{i,j}.$$

2. Frequency in interval $I_{i,j}$ is more frequent than in j-1, i.e. $d_{i,j} < d_{i,j-1}$

If the frequency in interval $I_{i,j}$ is more frequent than in $I_{i,j-1}$, i.e. $d_{i,j} < d_{i,j-1}$, then the number of expected tests will be calculated from the date that the recommended interval was changed.

The number of expected tests in interval $I_{i,i}$ is

$$n_{i,j} = floor\left(\frac{t_{i,j+1}-t_{i,j}}{d_{i,j}}\right),$$

and the last expected test during the interval is

$$m_{i,j} = t_{i,j} + d_{i,j}n_{i,j}.$$

The number of expected tests during the study period for participant i, N_i , is therefore the sum of the number of expected tests during each monitoring interval, i.e.

$$N_i = \sum_{j=0}^{c_i} n_{i,j}.$$

Example 1

Participant A has their HCT on March 1, 2020 and is discharged on May 1, 2020 ($t_{A,0}$). Their primary care physician would like them to continue CMV monitoring until 365 days post-HCT. Their recommended monitoring interval does not change during the study, i.e. $c_A = 0$. Their end of study date is $t_{A,1} = March 1, 2020 + 365 = March 1, 2021$.

Their recommended monitoring interval is $I_{A,0} = [t_{A,0}, t_{A,1}] = [May 1, 2020, March 1, 2021]$. The number of days between recommended monitoring tests is $d_{A,0} = 7$ in interval $I_{A,0}$.

The number of recommended tests in interval $I_{A,0}$, $n_{A,0}$, is

$$N_{A} = n_{A,0} = f loor\left(\frac{March\,1,2021 - May\,1,2020 + 1}{d_{A,0}}\right)$$
$$= f loor\left(\frac{305}{7}\right)$$

= 43

Example 2

Participant B has their HCT on March 1, 2020 and is discharged on May 1, 2020 ($t_{B,0}$). Their primary care physician would like them to continue CMV monitoring until 365 days post-HCT but recommends that they perform bi-weekly testing on $t_{B,1}$ = November 1, 2020. For participant B, the number of times

that their recommended monitoring interval is changed is $c_B = 1$. Their end of study date is $t_{B,2} =$ March 1, 2020 + 365 = March 1, 2021.

Their recommended monitoring intervals are

 $I_{B,0} = \left[t_{B,0}, t_{B,1}
ight]$ = [May 1, 2020, November 1, 2020] and

$$I_{B,1} = (t_{B,1}, t_{B,2}]$$
 = (November 1, 2020, March 1, 2021].

The number of days between recommended monitoring tests is $d_{B,0} = 7$ in interval $I_{B,0}$ and $d_{B,1} = 14$ in interval $I_{B,1}$.

The number of recommended tests in interval $I_{B,0}$, $n_{B,0}$, is

$$n_{B,0} = floor\left(\frac{November \, 1, \, 2020 - May \, 1,2020 + 1}{d_{B,0}}\right)$$
$$= floor\left(\frac{185}{7}\right)$$

= 26

The last recommended test during interval $I_{B,0}$ occurs on $m_{B,0} = May 1,2020 + 7 * 26 = \text{October 30, 2020.}$

The number of recommended tests in interval $I_{B,1}$, $n_{B,1}$, is

$$n_{B,1} = floor\left(\frac{\text{March 1,2021-October 30,2020}}{d_{B,1}}\right)$$
$$= floor\left(\frac{120}{14}\right)$$

= 8

Therefore, the number of expected tests during the study period for participant B is

 $N_B = \sum_{j=0}^{1} n_{B,j} = 26 + 8 = 34.$

Example 3

Participant C has their HCT on March 1, 2020 and is discharged on May 1, 2020 ($t_{C,0}$). Their primary care physician would like them to continue CMV monitoring until 365 days post-HCT however recommends that they perform bi-weekly testing on $t_{C,1}$ = November 1, 2020. Their physician recommends that they resume weekly testing for the remainder of the study period on January 20, 2021. For participant C, the number of times that their recommended monitoring interval is changed is $c_C = 2$. Their end of study date is $t_{C,3}$ = March 1, 2020 + 365 = March 1, 2021.

Their recommended monitoring intervals are

$$I_{C,0} = [t_{C,0}, t_{C,1}] = [May 1, 2020, November 1, 2020] and$$

$$I_{C,1} = (t_{C,1}, t_{C,2}]$$
 = (November 1, 2020, January 20, 2021], and

 $I_{C,2} = (t_{C,2}, t_{C,3}] = ($ January 20, 2021, March 1, 2021].

The number of days between recommended monitoring tests is $d_{C,0} = 7$ in interval $I_{C,0}$, $d_{C,1} = 14$ in interval $I_{C,1}$ and $d_{C,2} = 7$ in interval $I_{C,2}$.

Interval $I_{C,0}$:

The number of recommended tests in interval $I_{C,0}$, $n_{C,0}$, is

$$n_{C,0} = floor\left(\frac{November 1, 2020 - May 1,2020 + 1}{d_{C,0}}\right)$$
$$= floor\left(\frac{185}{7}\right)$$

= 26

The last recommended test during interval $I_{C,0}$ occurs on

$$m_{C,0} = May 1,2020 + 7 * 26 =$$
October 30, 2020.

Interval $I_{C,1}$:

The number of recommended tests in interval $I_{C,1}$, $n_{C,1}$, is

$$n_{C,1} = floor\left(\frac{\text{January 20,2021-October 30,2020}}{d_{C,1}}\right)$$
$$= floor\left(\frac{80}{14}\right)$$

= 5

The last recommended test during interval $I_{C,1}$ occurs on

 $m_{C,1} = October \ 30, 2020 + 14 * 5 = January 8, 2021.$

Interval $I_{C,2}$:

The number of recommended tests in $I_{C,2}$, $n_{C,2}$, is

$$n_{C,2} = floor\left(\frac{t_{C,3}-t_{C,2}}{d_{C,2}}\right)$$
$$= floor\left(\frac{March 1,2021 - January 20, 2021}{7}\right)$$
$$= floor\left(\frac{40}{7}\right)$$

= 5

Therefore, the number of expected tests during the study period for participant C is $N_C = \sum_{j=0}^{2} n_{C,j} = 26 + 5 + 5 = 36.$

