11 STATISTICAL CONSIDERATIONS

11.1 Study Outcome Measures

11.1.1 Primary Endpoint

The primary endpoint will be the proportion of subjects who complete >90% of their recommended CMV monitoring tests by 1-year post-transplant. We will use logistic regression modeling to compare this proportion between subjects randomized to DBS testing versus standard office-based testing. Since randomization will be stratified by transplant site and subject's perceived ease of access to blood draw facility, these factors will be used as adjustment factors in the models.

For each subject, the number of CMV monitoring tests performed will be assessed and the percent of recommended tests will be calculated. Subjects with percent completion >90% will be considered a success with regard to the primary endpoint. The personspecific denominator for the proportion, number of expected CMV monitoring tests, will be variable and dependent on subjects' immunosuppression and hospitalizations during the study. For example, subjects in this study that are highly immunosuppressed a weekly monitoring schedule is generally recommended, often throughout the first year after transplantation. If such a subject were discharged from the primary transplant center at day 100, there would be 38 remaining tests until day 365 after HCT (if the subject is still alive at 1 year). We will assess the actual number of tests performed and calculate the percent of tests (e.g. 36/38 = 94.7%). Another scenario would be for a subject that stopped monitoring and was then re-started on high-dose steroids for treatment of GVHD with resumption of weekly testing, resulting in yet another denominator. Study participants in the DBS arm who are hospitalized during the study should not collect DBS samples while admitted. Rather, admitting hospitals should monitor participants for CMV with plasma CMV DNA PCR testing as recommended for their level of immunosuppression. Those inpatient testing timepoints will not be included in the person-specific denominator.

The primary analysis will be an intent-to-treat (ITT) analysis of all subjects randomized. Another key analysis will be the modified intent to treat analysis of all subjects who had at least one test done after discharge from the primary transplant team.

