3.3.4. Number of Clinician-Recommended CMV Monitoring Tests Expected

At discharge, the clinician-recommended CMV monitoring schedule is anticipated to be weekly, however during the course of the study the participant's clinical team may recommend that monitoring become less frequent, for example at bi-weekly, monthly, quarterly or other schedules. The recommended monitoring schedules and the dates on which they come into effect are entered into the data system on the Visit Documentation electronic Case Report Form (eCRF) at discharge, each quarterly contact, or as needed between quarterly contacts, during medical chart abstraction. Letting *d* represent the number of days between clinician recommended CMV monitoring tests in the new schedule, the number of expected tests will be calculated using the following assumptions:

- 1. The first expected test occurs d days after discharge.
- 2. If the monitoring frequency is reduced, then the first test for the next schedule is expected d days after the last expected test in the previous interval.
- 3. If the monitoring frequency is increased, then the first test for the new schedule is expected d days after the date that the recommended interval was changed.

The number of expected tests during the study period for a given participant is the sum of the number of expected tests during each monitoring schedule over the course of the study period (defined in Section 3.3.2). Detailed information for the calculations of the number of expected tests can be found in Appendix 4.

At the University of Minnesota, the clinician recommended CMV monitoring schedule was not recorded, so this site entered the actual number of monitoring tests instead. These data will be used for the primary adherence analysis in the ITT population. A sensitivity analysis will be conducted to exclude all participants from the University of Minnesota for the primary and secondary adherence measures along with the local provider CMV monitoring interval recommendations summary (See Section 6.4, Section 8, and Section 14 for further details).

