3.3.5. Number of Clinician-Recommended CMV Monitoring Tests Completed

The clinician-recommended CMV monitoring tests actually completed are entered into the data system on the CMV Test Results (CTR) – Chart Review eCRF. The number of tests completed will be the number of records entered on this eCRF that were collected on or prior to the end of follow up date or, as a sensitivity analysis, the maximal possible study period end date.

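### SAP Appendix 4 is ambiguous about expected tests when monitoring stops and restarts, and the completed-test count has no matching cut while monitoring is stopped

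*SAP*

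**What the plan says.** Protocol 11.1.1 makes the number of expected tests specific to the person. As one scenario with its own denominator it names "a subject that stopped monitoring and was then re-started on high-dose steroids for treatment of GVHD with resumption of weekly testing".

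SAP 3.3.4 defines the total as the "sum of the number of expected tests during each monitoring schedule over the course of the study period". Its third rule reads "If the monitoring frequency is increased, then the first test for the new schedule is expected d days after the date" on which the interval was changed.

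SAP Appendix 4 turns this into formulas. Item 2 counts the times the "recommended monitoring interval was changed by their primary care physician during the study period". Item 4 defines the end of the last interval, t_{i,c_i+1}: "This is the earlier of the end of the study period or the date after which recommended monitoring is no longer required". Item 5 lists the spacings d, which "take the value 7 if recommended frequency is weekly, 14 if the frequency is bi-weekly, 30 if the frequency is monthly", then 90, 3.5 and 17.5. It gives no value for the No Further Monitoring Required category, although SAP 3.3.7 ranks that category as the least frequent interval. None of the three worked examples contains a stop; Example 3 goes from weekly to bi-weekly and back to weekly.

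The numerator is in SAP 3.3.5: the records on the chart-review form that were "collected on or prior to the end of follow up date". A sensitivity analysis uses the end of the maximal possible study period instead. No cut is made for time when monitoring was not recommended.

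**The concern.** The two halves of the ratio use different windows. The denominator has no expected tests while monitoring is stopped and, on the literal wording of item 4, none after it resumes. The numerator keeps counting throughout. A participant can therefore make up missed recommended tests with tests that nobody recommended. On the literal wording, a participant can also skip every resumed test without penalty. Success means more than 90%, so a few tests can change a participant's status.

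The protocol singles out the restart case because it follows renewed steroid treatment for GVHD. The programmer should not have to choose a rule for it, least of all in an unblinded trial. The secondary analysis is exposed too: SAP 8.2 describes the fractional logistic model as one for proportions between 0 and 1, and the plan has no rule for a larger value.

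**Working it through.** **1. The plan's own figures reproduce.** The formulas are n_0 = floor((t_1 − t_0 + 1)/d_0) for the first interval, floor((t_{j+1} − m_{j−1})/d_j) after a decrease in frequency, and floor((t_{j+1} − t_j)/d_j) after an increase.

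- Example 1: floor(305/7) = 43.
- Example 2: floor(185/7) + floor(122/14) = 26 + 8 = 34.
- Example 3: floor(185/7) + floor(82/14) + floor(40/7) = 26 + 5 + 5 = 36.
- Protocol 11.1.1, day 100 to day 365: floor(266/7) = 38.

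Appendix 4 prints 120 and 80 days where its dates give 122 and 82. The rounded-down results are the same.

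**2. Stop and restart.** The dates are my assumption: discharge day 100, weekly; stopped day 180; weekly again from day 270; end day 365.

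- Before the stop: floor((180 − 100 + 1)/7) = floor(81/7) = 11.
- After the restart: floor((365 − 270)/7) = floor(95/7) = 13.
- Item 4 read as the first stop: 11 expected.
- Item 4 read as the final stop, gap counted as zero: 11 + 0 + 13 = 24 expected.

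The first reading omits 13/24 = 54% of the expected tests. With Appendix 4's discharge and end dates (1 May 2020, 1 March 2021) and other assumed gaps:

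| Stop | Restart | First stop | Final stop | Omitted |
|---|---|---|---|---|
| 1 Jul | 1 Sep | 8 | 33 | 76% |
| 1 Aug | 1 Oct | 13 | 34 | 62% |
| 1 Nov | 20 Jan | 26 | 31 | 16% |
| 1 Dec | 1 Feb | 30 | 34 | 12% |

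**3. The first-stop reading breaks the notation.** Under item 2 a restart is a change, so its date must come before t_{i,c_i+1}. If that end date is set to the stop, the last interval is (270, 180] and its formula gives floor((180 − 270)/7) = −13.

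**4. The final-stop reading leaves the gap undefined.** If the stop is a change, the decrease formula needs a d value that item 5 does not supply. If it is not a change, weekly follows weekly, and the appendix covers only a larger or a smaller d. Running the first interval through the gap would give floor((270 − 100 + 1)/7) + 13 = 24 + 13 = 37, which includes tests nobody recommended.

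**5. The numerator, on either reading.** Take a participant who stops at day 180 and never restarts. The denominator is 11 on both readings.

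- 8 tests before the stop and 3 after it: (8 + 3)/11 = 100%, a success. Counting only recommended time, 8/11 = 73%, a fail.
- 11 before and 1 after: 12/11 = 109%, outside 0 to 1.

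Now take the restart case with all 24 expected tests in the denominator, 19 of them done and 3 more done during the gap: 22/24 = 92%, a success, against 19/24 = 79%, a fail.

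**6. Only if item 4 is read as the first stop.** Eleven early tests and none of the 13 resumed score 11/11 = 100% against 11/24 = 46%. Six early and all 13 resumed score 19/11 = 173% against 19/24 = 79%.

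**The case against.** A reader might infer that tests due after a restart are never counted and that the primary endpoint is therefore wrong for these participants. The documents do not settle that. Item 4 defines the end of the last interval, after all changes, and item 2 counts changes over the whole study period. SAP 3.3.4 sums over every schedule, and its third rule starts counting afresh after an increase. SAP 3.3.7 makes No Further Monitoring Required a ranked category, so leaving it for weekly testing is an increase. SAP 6.5.1 fails a participant with that category at discharge only if it is never changed. The increase formula needs neither a d value for the gap nor the last test before it, and it returns the 13 resumed tests. This stands: the final-stop reading is the more coherent one, and the contrasts in step 6 depend on the other.

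It can also be said that 3.3.5 describes its records as clinician-recommended tests, which would exclude tests done during a stop. That stands only in part. The operative rule counts records on the form up to a date. Protocol 7.5 has sites collect office-based CMV test dates and results without limiting them to recommended time. Nothing tells the programmer to remove the others.

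**Conclusion.** The point holds as an ambiguity in the denominator and a mismatch in the numerator. Item 4, taken literally, conflicts with protocol 11.1.1 and SAP 3.3.4. The rest of the SAP favours counting resumed tests, but the appendix gives no rule or example for the gap. The numerator mismatch does not depend on how item 4 is read: 3.3.5, applied as written, lets tests done outside recommended time offset missed ones and can push the proportion above 1.

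The sizes rest on assumed dates and test counts. They show that one participant's status can flip, not how often it will. The documents do not say how many participants stop or restart, so the effect on either arm, and its direction, cannot be computed. For scale, one changed status moves the planned control arm of 50 by 2 percentage points and the DBS arm of 100 by 1. The rule should be settled before the final analysis.

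**What to change.** In Appendix 4:

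- Define t_{i,c_i+1} as the end of the study period and drop the reference to monitoring no longer being required.
- Treat No Further Monitoring Required as an interval with zero expected tests.
- Count a restart from its change date under the third rule of 3.3.4.
- Add a stop-and-restart worked example. The dates in step 2 would serve, with 11 + 0 + 13 = 24.

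In 3.3.5, count completed tests only when they fall inside an interval with a recommended schedule, and apply the same rule to the maximal-period sensitivity analysis. Surplus tests inside a recommended interval could still take the proportion above 1, so the same edit should say how that is handled.

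The cost is SAP wording and programming. By 3.3.4, schedules and the dates they take effect are already entered on the Visit Documentation form, so no new data are needed.
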